- TIL: Tumor infiltrating lymphocyte
- tk: Thymidine kinase
- TLR: Toll-like receptor
- TNBC: Triple negative breast cancer
- TNF- α : Tumor necrosis factor- α
- Treg: Regulatory T cell
- TTP: Thrombotic thrombocytopenic purpura
- ULN: Upper limit of normal
- VZV: Varicella-zoster virus
- WBC: White blood cell
- WOCBP: Women of childbearing potential

Glossary of terms

Assessment	A procedure used to generate data required by the study
Baseline	For efficacy evaluations, the baseline assessment will be the last available assessment before or on the date of randomization. For safety evaluations (i.e. laboratory assessments and vital signs), the baseline assessment will be the last available assessment before or on the start date of study treatment. The value obtained at baseline assessments, referred to as "baseline value" will be used as reference for the patient.
Control drug	A study treatment used as a comparator to reduce assessment bias, preserve blinding of investigational drug, assess internal study validity, and/or evaluate comparative effects of the investigational drug
Dose level	The dose of drug given to the patient (total daily or weekly etc.)
Enrollment	Point/time of patient entry into the study; the point at which informed consent must be obtained (i.e. prior to starting any of the procedures described in the protocol)
Investigational drug	The study treatment whose properties are being tested in the study; this definition is consistent with US CFR 21 Section 312.3 and is synonymous with "investigational new drug."
Investigational treatment	Drug whose properties are being tested in the study as well as their associated placebo and active treatment controls (when applicable). This also includes approved drugs used outside of their indication/approved dosage, or that are tested in a fixed combination. Investigational treatment generally does not include other study treatments administered as concomitant background therapy required or allowed by the protocol when used in within approved indication/dosage
Medication number	A unique identifier on the label of each study treatment package which is linked to one of the treatment groups of a study
Other study treatment	Any drug administered to the patient as part of the required study procedures that was not included in the investigational treatment
Patient	A unique identifying number assigned to each patient/subject/healthy volunteer who enrolls in the study

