A screening medical history and physical exam will be performed (baseline symptom-medical history and physical examination are not required if the screening was conducted within 7 to 28 days prior to day 0 of ADV/HSV-tk). Patients presenting with any medical history, physical exam, or laboratory abnormality that, in the opinion of the treating physician, would put their safety at risk will be excluded. A window of ± 5 days is allowed for study visits and assessments (except as otherwise specified). A physical exam will be performed on days 0 and 17; every 4 weeks thereafter until completion of the protocol-specified treatment; and at end of treatment (EOT). Vital sign (blood pressure, heart rate, and oral temperature) measurements will be performed at each physical exam. A 12-lead electrocardiogram (ECG) will be performed at screening, at EOT, and when clinically indicated. Multigated acquisition (MUGA) scan or echocardiogram (ECHO) will be performed when clinically indicated. The same method (ECHO or MUGA scan) must be used throughout the duration of the study. A blood sample for complete blood count (CBC) with platelet count and differential white blood cell (WBC) count will be obtained at screening, on days 0 and 17, every 4 weeks thereafter until completion of the protocol-specified treatment, at EOT, and when clinically indicated. If a patient is found to have an absolute neutrophil count (ANC) $< 1.5 \times 10^9/L$, platelet count $< 100 \times 10^9/L$, or both, the CBC with differential should be repeated at least every other day until the ANC and platelet count have exceeded these values. A blood sample for clinical chemistry panel (glucose, albumin, sodium, potassium, carbon dioxide, chloride, blood urea nitrogen [BUN], creatinine, total bilirubin, alkaline phosphatase, aspartate transaminase [AST], and ALT) and evaluation of magnesium and lactate dehydrogenase will be obtained at screening, on days 0 and 17, every 4 weeks thereafter until completion of the protocol-specified treatment, at EOT, and when clinically indicated. Prothrombin time (PT), international normalized ratio (INR), and activated partial thromboplastin time (aPTT) testing will be performed at screening, on day 17, every 4 weeks thereafter until completion of the protocol-specified treatment, and at EOT. For women of childbearing potential (WOCBP), the results of a serum β -human chorionic gonadotropin (β -hCG) pregnancy test must be negative within 7 days of the administration of the first treatment dose. If the screening serum β -hCG pregnancy test is performed more than 7 days before ADV/HSV-tk dosing, it must be repeated at baseline, with results known to be negative prior to the administration of the first dose of the study treatment. Serum β -hCG pregnancy testing is to be repeated as clinically indicated. Laboratory tests may be done more frequently if medically indicated. Patients will be assessed for AEs and SAEs from informed consent signing up to and including 30 days after the last treatment dose. Study treatment-related AEs occurring beyond 30 days after the last dose of nivolumab and any study patient death should also be reported. Toxicity will be defined as any treatment-related death or any \geq Grade 3 toxicity excluding alopecia and constitutional symptoms as assessed by NCI CTCAE v4.03. Patients whose treatment is interrupted or permanently discontinued due to an AE including

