- Histologically or cytologically confirmed stage IV metastatic squamous or non-squamous NSCLC that has progressed after a platinum-based chemotherapy and after a single-agent immunotherapy **OR** histologically or cytologically confirmed metastatic uveal melanoma that is immunotherapy naïve.
- Evaluable or measurable disease as per RECIST 1:1, a target lesion of suitable diameter (at least 5 mm) for SBRT, and a non-target lesion of at least 1 cm in diameter for abscopal effect evaluation.
- ≥ 4 weeks since any major surgery.
- A 2-week washout period post any prior systemic anticancer therapy, RT, and/or investigational therapy is required prior to trial entry. Subject should be adequately recovered from the acute toxicities of any prior therapy.
- Life expectancy ≥ 6 months.
- ECOG performance status of 0–1.
- Adequate bone marrow function:
 - ANC $\geq 1.5 \times 10^9/L$ (without granulocyte colony stimulating factor support within 2 weeks of laboratory test used to determine eligibility)
 - Platelets $\geq 100 \times 10^9/L$ (without transfusion within 2 weeks of laboratory test used to determine eligibility)
 - Hemoglobin $\geq 8 \text{ g/dL}$ (without blood transfusion)
 - WBC count $> 2,500/\mu L$ and $< 15,000/\mu L$
 - Lymphocyte count $\geq 500/\mu L$
- Adequate liver function:
 - Serum bilirubin $\leq 1.0 \times \text{ULN}$ (patients with known Gilbert's disease who have serum bilirubin level $\leq 3 \times \text{ULN}$ may be enrolled)

- Serum transaminases (AST or ALT) activity $\leq 2.5 \times$ ULN with normal alkaline phosphatase (patients with liver metastases $\leq 5 \times$ ULN) OR AST and ALT $\leq 1.5 \times$ ULN with an alkaline phosphatase $> 2.5 \times$ ULN
- INR or PT and aPTT $\leq 1.5 \times$ ULN (unless patient is receiving anticoagulant therapy as long as PT or aPTT is within therapeutic range of intended use of anticoagulants);
- Adequate renal function: serum creatinine $< 2 \times$ ULN.
- WOCBP must have a negative serum pregnancy test within 7 days prior to the administration of the first study treatment. Women must not be lactating.
- WOCBP and men must practice an effective method of birth control (See Section 12.5).
- Signed informed consent to participate in the study must be obtained from patients after they have been fully informed of the nature and potential risks of the study by the investigator (or his/her designee) with the aid of written information.
- Willing to provide biopsies as required by the study.

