9.4 Nivolumab

Common trade name(s): Opdivo®

Classification: monoclonal antibody

Mechanism of action:

Nivolumab is a fully human immune checkpoint inhibitor monoclonal antibody. Nivolumab enhances antitumor immunity by selectively blocking the interaction of PD-1 with its known ligands, PD-L1 and PD-L2, disrupting the negative regulation of T cell activation and proliferation.^{182, 183}

Uses:

Primary uses: Melanoma,¹⁸⁴ Lung cancer, Squamous and non-squamous NSCLC¹⁸⁵

Other uses: Renal cell cancer,^{186,187} Hodgkin's lymphoma¹⁸⁸

Special precautions:

Pregnancy: In animal reproduction studies, nivolumab administration resulted in increased abortion and premature infant death. There is no available human data; however, a central function of the PD-1/PD-L1 pathway is to preserve pregnancy by maintaining maternal immune tolerance to the fetus. Therefore, based on its

mechanism of action, nivolumab may cause fetal harm if administered to a pregnant woman. Also, human IgG4 is known to cross the placental barrier. As nivolumab is an IgG4 antibody, it has the potential to be transmitted from the mother to the developing fetus where it may increase the risk of immune-mediated disorders. WOCBP are advised to use effective contraception during treatment and for five months following the last dose of nivolumab.

Side effects:

The table below includes AEs that presented during drug treatment but may not necessarily have a causal relationship with the drug. Because clinical trials are conducted under very specific conditions, the AE rates observed may not reflect the rates observed in clinical practice. AEs reported in more than 1% of patients in the product monograph or pivotal trials are included.

Table 6. Nivolumab side effects

ORGAN SITE	SIDE EFFECT
Gastrointestinal	Emetogenic potential: low, Abdominal pain (16%, severe 2%), Constipation (24%), Nausea (29%, severe 2%), Vomiting (19%, severe 1%).
General disorders and administration site conditions	Extravasation hazard: none, Asthenia (19%, severe 2%), Chest discomfort, non-cardiac chest pain (13%), Edema (17%, severe 2%), Fatigue (50%, severe 7%), Peripheral edema (10%), Pyrexia (17%).
Immune system (see paragraph following Side Effects table)	Colitis (1-2%), Diarrhea (18-21%, severe 1-3%), Hepatitis (1%), Hyperthyroidism (2-3%), Hypothyroidism (4-8%), Nephritis, renal dysfunction (1%), Pneumonitis (1-6%).
Infections and infestations	Upper respiratory tract infection (11%)

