Investigations	Alkaline phosphatase increase (14-22%), ALT increase (12-16%), AST increase (16-28%), Total bilirubin increase (3-19%), Creatinine increase (13-22%), Weight decrease (13%, severe 1%).
Metabolism and nutrition	Decreased appetite (35%, severe 3%).
Musculoskeletal and connective tissue	Arthralgia (13%), Musculoskeletal pain (36%, severe 6%).
Respiratory, thoracic, and mediastinal	Cough (17%).
Skin and subcutaneous tissue	Pruritus (19%), Rash (21%, severe <1%).

Clinically significant immune-mediated adverse reactions can occur, including pneumonitis, colitis, hepatitis, nephritis, hypothyroidism, and hyperthyroidism. Immune reactions may be delayed or occur after nivolumab discontinuation. Based on the type and severity of the reaction, management may include withholding or discontinuing nivolumab, administering HD corticosteroids, and if appropriate, initiating hormone replacement therapy. Following resolution of the reaction to grade 1 or less, corticosteroids should be tapered over at least one month. Nivolumab should not be resumed while the patient is receiving immunosuppressive doses of corticosteroids or other immunosuppressive therapy. Restarting nivolumab may be considered following completion of corticosteroid taper. Permanent discontinuation of nivolumab is usually recommended following grade 3 or 4 immune-mediated reactions.

Supply and storage:

Injection: Bristol-Myers Squibb Company supplies nivolumab as 40 mg and 100 mg ready-to-use, single-use (preservative-free) vials in a concentration of 10 mg/mL. Refrigerate and store in original packaging to protect from light. Do not freeze or shake.¹⁸⁹

Solution and compatibility:

- Nivolumab should be clear and colorless to pale-yellow in color. Discard if cloudy or discolored.
- Nivolumab can be infused undiluted (10 mg/mL) or diluted with normal saline or 5% dextrose in water (to 0.35 mg/mL or greater).

Parenteral administration:

Intermittent infusion over 60 minutes.

Dosage guidelines:

The ENSIGN protocol's guidelines for dosing also include consideration of ANC. Dosage may be reduced, delayed, or discontinued in patients with bone marrow depression due to cytotoxic therapy/RT or other toxicities. (See Section 6 for management of immune-mediated complications of nivolumab)

Table 7. Nivolumab adult dosing

Route	Cycle Length:	Dose
IV	4 weeks	480 mg IV for one dose on day 1 (Total dose per cycle, 480 mg)

Table 7

10. Prohibited concomitant therapy

Antineoplastic therapies

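### No thyroid function test is scheduled at screening, before nivolumab or on treatment, so undiagnosed or early thyroid dysfunction has no pre-treatment value in either cohort

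*Combined protocol and SAP*

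**What the plan says.** The chemistry panel is written out three times: in Section 7 (Safety Criteria), in the footnotes to the Section 11 visit schedule, and in Section 12. Each time it is the same 12 analytes plus two more, with the timing "evaluation of magnesium and lactate dehydrogenase will be obtained at screening, on days 0 and 17, every 4 weeks thereafter" and again at EOT. The other scheduled laboratory work is blood count, coagulation, serum pregnancy test and correlative samples. TSH, T3 and T4 appear nowhere in these lists, in the visit table, or in the eligibility laboratory criteria of Section 8.1.

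Section 9.4 says of nivolumab: "Clinically significant immune-mediated adverse reactions can occur, including pneumonitis, colitis, hepatitis, nephritis, hypothyroidism, and hyperthyroidism". It adds "Immune reactions may be delayed or occur after nivolumab discontinuation", and among the possible responses it gives "if appropriate, initiating hormone replacement therapy". Table 6 lists hyperthyroidism at 2–3% and hypothyroidism at 4–8%, with the caution that tabulated events "may not necessarily have a causal relationship with the drug".

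Three other provisions bear on the point:

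- The glossary ties the laboratory baseline to the day the study regimen begins: "For safety evaluations (i.e. laboratory assessments and vital signs), the baseline assessment will be the last available assessment before or on the start date".
- Section 8.2 excludes uncontrolled hypothyroidism, as one of several diseases that could prolong QT. It prescribes no test.
- Section 8.1 admits NSCLC "that has progressed after a platinum-based chemotherapy and after a single-agent immunotherapy". Section 8.2 asks only for 2 weeks between immunotherapy and study treatment. Uveal melanoma patients must be immunotherapy naive.

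**The concern.** The plan names a reaction, gives its frequency and anticipates its treatment, but schedules no test that would find it before symptoms do. Other organs are handled differently. Table 6 puts hepatitis and nephritis at 1% each, and the panel follows liver and kidney function at every nivolumab visit. The thyroid reactions are listed as more frequent and have no scheduled test.

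The missing pre-treatment value matters most because it cannot be obtained afterwards. A test ordered once symptoms appear shows the current state, not the state at entry. Three things are at stake:

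- Early dysfunction may be found late.
- The uncontrolled-hypothyroidism exclusion can be applied only to disease someone already knows about or suspects.
- Section 15 promises the frequency of laboratory abnormalities. For thyroid function, that frequency would depend on who happened to be tested.

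The NSCLC cohort is the more exposed, because those patients may bring dysfunction from the earlier immunotherapy with them.

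**Working it through.** **1. Is the test really absent?** The three panel lists agree analyte for analyte: glucose, albumin, sodium, potassium, carbon dioxide, chloride, BUN, creatinine, total bilirubin, alkaline phosphatase, AST and ALT, then magnesium and LDH. The visit table has no thyroid row. Three complete and matching lists make a text-extraction fault or redaction an unlikely explanation.

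**2. Does it touch the design figures?** The plan gives no figure on thyroid testing to reproduce. Its power figures (Section 15.1) do reproduce with exact binomial tails:

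- NSCLC, n = 16: P(X ≥ 3 | 0.25) = 0.803, with P(X ≥ 3 | 0.03) = 0.011. The plan states 80.3%.
- Uveal melanoma, n = 9: P(X ≥ 2 | 0.30) = 0.804, with P(X ≥ 2 | 0.03) = 0.028. The plan states 80.4%.

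No thyroid input enters either calculation.

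**3. How many thyroid events might occur?** Inputs are the Table 6 rates and the planned numbers, 16 + 9 = 25. Overlap between the two conditions is not given, so both extremes are shown.

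- Full overlap: the rate is the larger of the two, 4–8%.
- No overlap: 4 + 2 = 6% to 8 + 3 = 11%.
- Outer range for 25 patients: 25 × 0.04 = 1.0 to 25 × 0.11 = 2.75.
- NSCLC: 16 × 0.04 = 0.64 to 16 × 0.11 = 1.76.
- Uveal melanoma: 9 × 0.04 = 0.36 to 9 × 0.11 = 0.99.
- Chance of at least one hypothyroidism case in 25: 1 − 0.96^25 = 64% to 1 − 0.92^25 = 88%.

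If the rates hold only for the immunotherapy-naive cohort, 0.36–0.99 is all that these inputs support.

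**4. Timing.**

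- Shortest gap from prior immunotherapy to first nivolumab: 14 + 17 = 31 days (30 with the −1 day window). This is a minimum, not a typical value.
- Oldest screening value at day 0: 28 days.
- Oldest screening value at first nivolumab: 28 + 17 = 45 days (46 with the +1 day window).

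**5. What would a baseline value tell us?**

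- Abnormal at entry: the dysfunction was already present and is not a new on-study event.
- Normal at entry, abnormal later, NSCLC: new since entry, but a delayed effect of the prior agent remains possible. The documents describe delayed reactions for nivolumab only and do not name the prior agent, so that possibility is an assumption.
- Normal at entry, abnormal later, uveal melanoma: new since entry, with no prior immunotherapy to compete as an explanation.

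A day-17 value follows vector, valacyclovir and SBRT. It is a useful pre-nivolumab reference, but it is not the glossary baseline, which closes at the start of study treatment.

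**The case against.** The strongest reply is that thyroid disease is not ignored. Known disease goes into medical history. Uncontrolled hypothyroidism is excluded, and Section 7 makes the investigator responsible for checking exclusions. Patients should have recovered from acute toxicities of earlier therapy. Examinations with heart rate take place on days 0 and 17 and every 4 weeks, adverse events are asked about at each visit, and extra laboratory tests are allowed on medical grounds. This stands for known and symptomatic disease. A reader might infer that thyroid toxicity goes wholly unmonitored; the documents do not support that. The reply does not reach undiagnosed or early dysfunction, and none of these provisions yields a pre-treatment value.

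A second reply concerns attribution. A reader might infer that a baseline TSH would separate a study-drug event from an effect of the prior agent. It would not do so by itself: if delayed effects of that agent are possible, a normal entry value followed by a later abnormality stays ambiguous. Section 13.1.1 also lets the investigator grade the relationship as uncertain. The benefit is limited to recognising dysfunction already present at entry.

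A third reply is that routine testing could do harm through Section 6, which calls for prednisone and withholding of nivolumab for Grade 2 immune-mediated complications, while an interruption beyond 21 days ends study treatment. Section 6 defines such complications by the need for corticosteroids, so hypothyroidism managed with hormone alone probably falls outside it, but the wording is not explicit. This point stands, and the change should settle it.

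Finally, no section sets a frequency for thyroid testing, so the on-treatment interval is a matter of judgement for the sponsor.

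**Conclusion.** The omission is real, and the plan should be changed. Followed exactly, it leaves undiagnosed or early thyroid dysfunction untested in both cohorts, with no pre-treatment value that could be recovered later. The relevance is greatest in NSCLC because of the prior immunotherapy.

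The scale is about 1.0 to 2.75 thyroid events in 25 patients, assuming the Table 6 rates carry over to this trial. Those rates are not necessarily causal. It is tempting to read the figure as events the plan would miss. It counts events occurring; the documents give nothing from which to estimate how many would be missed, found late or misattributed.

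Nor does the gap bear on the efficacy conclusion: ORR, power, alpha and the Grade 3 or greater run-in rule are unaffected. Confidence is high that the test is absent. The size of the consequence is unknown.

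**What to change.** - **Baseline.** Add TSH, with free T4 if abnormal, to the existing screening draw, or to the day-0 draw with the result known before dosing. This supplies the glossary baseline and helps apply the uncontrolled-hypothyroidism exclusion. It is the essential part.
- **Later values.** Repeat TSH on the existing day-17 draw as a pre-nivolumab value, then periodically at existing nivolumab visits and at EOT, at an interval the sponsor chooses.
- **Section 6.** State that hypothyroidism managed with hormone replacement alone is not an immune-mediated complication requiring corticosteroids.

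The change needs protocol and CRF wording but no new visit or draw. The TSH count depends on the interval, taking 52 / 4 = 13 nivolumab visits in 12 months:

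- Screening and day 17 only: 2 × 25 = 50.
- Screening, every second nivolumab visit, EOT: (1 + 7 + 1) × 25 = 225.
- Screening, every nivolumab visit, EOT: (1 + 13 + 1) × 25 = 375.

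The last two are upper limits, since patients who progress early will have fewer. Free T4 tests triggered by an abnormal TSH are extra, and some mild incidental abnormalities will need follow-up.

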- To estimate the clinical benefit rate (CBR) of ADV/HSV-tk + Valacyclovir therapy in combination with SBRT used as a window of opportunity treatment before nivolumab in patients with metastatic squamous or non-squamous NSCLC and metastatic uveal melanoma.

Exploratory Objectives:

- To determine the abscopal effect of ADV/HSV-tk + Valacyclovir therapy in combination with SBRT. The primary criterion for abscopal effect evaluation will be computed tomography (CT)-based response assessment of a non-targeted lesion. The secondary criterion will be immune parameters including PD-1 and PD-L1 expression, immune infiltrates, and cytokine expression (IL-1, IL-2, IL-6, IL-12, IFN- γ , TNF- α , and GM-CSF).
- To measure the immune response to nivolumab in patients with squamous or non-squamous NSCLC and metastatic uveal melanoma.
- To assess the Th1 (cellular-based) response by measuring the following cytokines: IL-1, IL-2, IL-6, IL-12, IFN- γ , TNF- α , and GM-CSF.
- To measure TILs before and after ADV/HSV-tk + Valacyclovir therapy.
- To explore correlative tissue and blood-based biomarkers of treatment response including but not limited to T-cell cytokine profiles (IL-1, IL-2, IL-6, IL-12, IFN- γ , TNF- α , and GM-CSF), TILs, PD-1 and PD-L1 expression, effector and suppressor immunocyte populations.

Endpoints

Primary endpoint: The primary endpoint will be the ORR of ADV/HSV-tk + Valacyclovir therapy in combination with SBRT used as a window of opportunity treatment before nivolumab in patients with metastatic squamous or non-squamous NSCLC and metastatic uveal melanoma. Both RECIST 1.1 and modified irRC will be used to assess treatment response.

Secondary endpoints: Secondary endpoints will include a) DoR; b) OS and PFS rates; c) CBR; d) safety and toxicity (toxicity will be defined as any treatment-related death or any \geq Grade 3 toxicity excluding alopecia and constitutional symptoms as assessed by NCI CTCAE v4.03); e) immune-mediated antitumor activity (assessed by RECIST 1.1 and modified irRC); and f) correlative tissue and blood-based biomarkers of ADV/HSV-tk + Valacyclovir therapy in combination with SBRT used as a window of opportunity treatment before nivolumab.

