In the above clinical studies, patients that received immunotherapy plus ionizing RT were successfully immunized against their tumor, both locally and systemically. The standing question is whether more patients would have responded if their irradiated metastatic lesion had been ablated or if ablative doses of stereotactic radiosurgery had been applied to all clinically and radiologically detectable metastatic sites.

Dosage guidelines:

SBRT of 30 Gy (6 Gy X 5 fractions) will be administered over 2 weeks starting from day 2 to day 14 of the study.

Delivery:

Tumor target will be decided by PET/CT scan. For the planned dosing regimen, SBRT simulation will be done before treatment. For subjects with multiple tumors, the largest tumor will be selected. Sedation is not necessary for SBRT.

Side effects:

Side effects of the proposed low-dose SBRT will be minimal. Potential side effects include fatigue, skin irritation, esophagitis, pneumonitis, bronchitis, rib fracture, chest wall pain, and spinal cord injury.

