12.1 Criteria for response

The main endpoint in this study is the ORR of ADV/HSV-tk + Valacyclovir therapy in combination with SBRT used as a window of opportunity treatment before nivolumab in patients with metastatic squamous or non-squamous NSCLC and metastatic uveal melanoma. RECIST criteria 1.1 will be used to select patients with detectable or measurable disease as part of the initial inclusion process. Modified irRC and RECIST 1.1 will be used to assess treatment response.

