12.2 RECIST

RECIST offers a simplified, conservative, extraction of imaging data for wide application in clinical trials. They presume that linear measures are an adequate substitute for two-dimensional methods and register four response categories.¹⁹⁰

Target Lesions (Main Tumor)

- **Complete Response (CR):** Disappearance of all target lesions. Any pathological lymph nodes (whether target or non-target) must have reduction in short axis to <10 mm.
- **Partial Response (PR):** At least a 30% decrease in the sum of the diameters of target lesions, using the baseline sum diameters as the reference.
- **Progressive Disease (PD):** At least a 20% increase in the sum of the diameters of target lesions, using the smallest sum on study (includes the baseline sum) as the reference. In addition to the relative 20% increase, the sum must also demonstrate an absolute increase of at least 5 mm. (Note: the appearance of one or more new lesions is also considered progression)
- **Stable Disease (SD):** Neither sufficient shrinkage to qualify for PR nor sufficient increase to qualify for PD, using the smallest sum diameters while on study as the reference.

Non-Target Lesions (Lymph Nodes)

- **CR:** Disappearance of all non-target lesions and normalization of tumor marker levels. All lymph nodes must be non-pathological in size (<10 mm short axis).

Note: If tumor markers are initially above the upper normal limit, they must normalize for a patient to be considered in complete clinical response.

- Non-CR/Non-PD: Persistence of one or more non-target lesion(s) and/or maintenance of tumor marker levels above the normal limits.
- PPD: Appearance of one or more new lesions and/or *unequivocal progression* of existing non-target lesions. *Unequivocal progression* should not normally trump target lesion status. It must be representative of overall disease status change, not a single lesion increase.
- Although a clear progression of “non-target” lesions only is exceptional, the opinion of the treating physician should prevail in such circumstances, and the progression status should be confirmed at a later time by the review panel (or principal investigator).

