12.3 Modified irRC, derived from RECIST 1.1¹⁹¹

This new classification is based on recent clinical studies showing delays in tumor regression or stabilization with cancer immunotherapies. For the ENSIGN trial, the concepts of the irRC are combined with RECIST 1.1 to come up with the modified irRC, which uses unidimensional measurements. For modified irRC, only target and measurable lesions are taken into account. In contrast to RECIST 1.1, the modified irRC criteria (a) require confirmation of both progression and response by imaging at eight 8 weeks after initial imaging (evidence of cancer progression within the first 3 months on bone scan only should be interpreted with extreme caution due to risk of tumor flare) and (b) do not necessarily score the appearance of new lesions as PD if the sum of the diameters of target lesions (minimum of 10 mm per lesion, maximum of 5 target lesions, maximum of 2 per organ) and measurable new lesions does not increase by $\geq 20\%$. The same assessment method and technique should be used to characterize each identified and reported target lesion(s) at baseline, during the trial, and at EOT. All measurements should be recorded in metric notation. The modified irRC based on RECIST 1.1 are displayed below. Modified irRC are defined as follows:

- New measurable lesions: Incorporated into tumor burden.
- New non-measurable lesions: Do not define progression but preclude irCR.
- Overall irCR: Complete disappearance of all lesions (whether measurable or not) and no new lesions. All measurable lymph nodes also must have a reduction in short axis to 10 mm or less.
- Overall irPR: $\geq 30\%$ decrease in the sum of the longest diameters of target and new measurable lesions.
- Overall irSD: Neither sufficient shrinkage to qualify for irCR or irPR (compared to baseline) nor sufficient increase to qualify for irPD (compared to nadir), using the sum of the longest diameters of target and new measurable lesions.
- Overall irPD: $\geq 20\%$ increase in the sum of the longest diameters of target and new measurable lesions increases (compared to nadir), confirmed by a repeat, consecutive observation at least 6 weeks (normally it should be done at 8 weeks) from the date first documented.

Documentation of immune-related PD (based on modified irRC) does not mandate discontinuation of the study treatment even after irPD is confirmed with CT scan 6 weeks after the initial observation of irPD.

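### Entry does not require measurable disease although the primary endpoint is ORR, so a patient who cannot reach a partial response can be enrolled; separately, the lesion rules in 8.1 and 9.3 need reconciling for the abscopal objective

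*Combined protocol and SAP*

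**What the plan says.** **Entry.** Section 8.1 requires "Evaluable or measurable disease as per RECIST 1:1, a target lesion of suitable diameter (at least 5 mm) for SBRT" and, in the same sentence, "a non-target lesion of at least 1 cm in diameter for abscopal effect evaluation". Section 12.1 states the disease requirement again: "RECIST criteria 1.1 will be used to select patients with detectable or measurable disease as part of the initial inclusion process". In both places measurable disease is one of two alternatives.

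**Endpoint.** The primary endpoint in section 4 is ORR: "Both RECIST 1.1 and modified irRC will be used to assess treatment response".

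**Response criteria.** In 12.2, partial response is "At least a 30% decrease in the sum of the diameters of target lesions", taken from baseline. Non-target disease has no partial-response category; it is complete response, neither complete response nor progression, or progression. Section 12.3 says "For modified irRC, only target and measurable lesions are taken into account" and describes target lesions as "minimum of 10 mm per lesion, maximum of 5 target lesions, maximum of 2 per organ". Its partial response is again a 30% fall in a sum of longest diameters.

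**Choice of SBRT lesion.** Section 9.3 says "For subjects with multiple tumors, the largest tumor will be selected".

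**Analysis.** Section 15 gives power of 80.3% for 16 NSCLC patients and 80.4% for 9 uveal melanoma patients. It names no response-evaluable population, no replacement rule and no handling of patients without measurable disease.

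**The concern.** An ORR endpoint presumes that every patient in the denominator could show a partial or a complete response. The entry criteria do not secure this. A patient admitted on evaluable disease alone has no baseline sum of diameters, so the usual route to counting as a responder is closed. Because 8.1 and 12.1 both leave this open, it does not look like a slip in one sentence.

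The cohorts have 16 and 9 patients and their power sits just above 80%, so a single such patient matters. Section 15 does not say whether that patient would stay in the denominator as a non-responder or be left out, and that choice would be made after the data are seen.

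A second, smaller issue concerns lesion selection. Section 8.1 sets a lower size limit for the SBRT lesion than for the abscopal lesion, while 9.3 directs SBRT to the largest tumor. The two rules can point to the same lesion.

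**Working it through.** **1. Reproducing the stated power.** Inputs from 15.1: NSCLC n = 16, null rate 3%, alternative 25%; uveal melanoma n = 9, null 3%, alternative 30%; one-sided alpha 0.05. The plan names Fisher's exact test; the figures reproduce with the one-sample exact binomial test. The cut-off r is the smallest number of responders with P(X ≥ r | null rate) ≤ 0.05.

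- NSCLC: P(X ≥ 2 | 16, 0.03) = 0.0818, too large; P(X ≥ 3 | 16, 0.03) = 0.0113. So r = 3. Power = 1 − 0.75^16 − 16(0.25)(0.75^15) − 120(0.25^2)(0.75^14) = 1 − 0.0100 − 0.0535 − 0.1336 = 0.803.
- Uveal melanoma: P(X ≥ 1 | 9, 0.03) = 0.2398, too large; P(X ≥ 2 | 9, 0.03) = 0.0282. So r = 2. Power = 1 − 0.7^9 − 9(0.3)(0.7^8) = 1 − 0.0404 − 0.1556 = 0.804.

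Both agree with the plan.

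**2. Illustration with k evaluable-only patients.** Assume k patients cannot respond, count as non-responders, and the cut-offs stay at 3 of 16 and 2 of 9. Power is then P(X ≥ r | n − k, alternative rate). The documents give no value for k.

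| k | NSCLC (r = 3, rate 0.25) | Uveal melanoma (r = 2, rate 0.30) |
|---|---|---|
| 0 | 80.3% | 80.4% |
| 1 | 76.4% | 74.5% |
| 2 | 71.9% | 67.1% |

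Worked for one cell, uveal k = 1: 1 − 0.7^8 − 8(0.3)(0.7^7) = 1 − 0.0576 − 0.1976 = 0.745.

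**3. Allowing for complete responses.** Complete response stays possible without a sum. If each such patient has an assumed 0 to 5% chance of one, power at k = 2 is 71.9 to 73.7% (NSCLC) and 67.1 to 69.5% (uveal melanoma). The picture barely changes.

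**4. Leaving such patients out instead.** Re-deriving the cut-off at n − k gives the same power as in the table for k = 1 and 2. It is not always a loss: at k = 4 in NSCLC, n = 12 gives r = 2, alpha 0.0486 and power 84.2%. An unnamed denominator can therefore change the decision rule as well as the power.

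**5. Lesion rules side by side.** Take a patient with one 12 mm and one 5 mm lesion.

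- If the 5 mm lesion is the SBRT lesion and the 12 mm lesion the abscopal one, the size limits in 8.1 are met but the rule in 9.3 is broken.
- If 9.3 is followed, the 12 mm lesion is irradiated and the remaining 5 mm lesion is below the 1 cm that 8.1 sets for abscopal evaluation.
- If 8.1 and 9.3 are read jointly at screening, the patient fails entry, and the 5 mm limit does no work in a patient with several tumors.

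The text does not say which reading applies.

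**The case against.** A reader might infer that the 5 mm limit makes enrolled patients unscorable for ORR, since 12.3 sets 10 mm. The documents do not support this. Every eligible patient must also have a lesion of at least 1 cm. Nothing in 9.3, 12.2, 12.3 or Appendix D removes an irradiated lesion from the target sum, and 12.2 labels target lesions as the main tumor. If a 10 mm irradiated lesion shrinks to 7 mm and is the only target lesion, the fall is 3/10 = 30%, which meets the threshold. The 10 mm minimum is also written only for modified irRC; 12.2 gives no minimum for non-nodal lesions.

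It would likewise be too strong to say that evaluable-only patients cannot be scored. Under 12.2 they can still be rated complete response, progression, or neither. Only partial response is out of reach.

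The 1 cm requirement, together with the need for a lesion that can be injected and irradiated, also makes evaluable-only patients unlikely to be common. This stands, and it limits the expected size of the problem. It does not close the gap: 8.1 labels the 1 cm lesion as non-target and does not say it must be measurable, whereas 12.3 counts only target and measurable lesions.

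On the lesion rules, the joint reading in which the 12 mm and 5 mm patient fails screening is fair. If it is intended, no abscopal assessment is lost. The objective concerned is exploratory in any case.

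**Conclusion.** The concern holds in a limited form. The entry wording in 8.1 and 12.1 does not match an ORR endpoint whose partial response needs a sum of lesion diameters. The defect comes from the evaluable and detectable alternatives, not from the 5 mm figure.

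Its size is conditional. Each of the first two such patients costs about 4 to 5 points of power in NSCLC (3.9, then 4.5) and about 6 to 7 in uveal melanoma (5.9, then 7.4), if they count as non-responders and the cut-offs are unchanged. The number of such patients is an assumption and may be zero. A reader might infer that the trial is underpowered as planned; the documents do not show that, and the stated powers are correct if every patient has measurable disease.

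The tension between 8.1 and 9.3 is real on one reading. It affects only the exploratory abscopal assessment, not the primary endpoint.

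**What to change.** 1. In 8.1, delete the evaluable alternative and require at least one lesion measurable under RECIST 1.1 and section 12.3. One is enough for ORR; a two-lesion rule is not needed for that purpose.
2. Align 12.1, so that measurable disease is required there too.
3. Reconcile 8.1 with 9.3, so that the lesion of at least 1 cm kept for abscopal evaluation is one that is neither injected nor irradiated. Which lesion is treated is for the sponsor to decide.

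The cost is an amendment to a few sentences and slightly narrower eligibility, limited because a lesion of at least 1 cm is already required. No change in sample size is needed: with measurable disease in every patient, no power is lost through this route and the stated 80.3% and 80.4% stand.
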